#### 11.5.2 Laboratory Data

The following safety laboratory data will be collected for this study:

- Routine hematology [red blood cell count, hemoglobin, hematocrit, red cell indices, white blood cell count (including differential), platelet count], coagulation [prothrombin time (PT), international normalized ratio (INR), activated partial thromboplastin time (APTT)] and biochemistry evaluations [Sodium, potassium, chloride, urea, creatinine, calcium, inorganic phosphate, glucose, total bilirubin, total protein, albumin, aspartate aminotransferase, alanine aminotransferase, alkaline phosphatase, Gamma-glutamyl Transferase (Gamma GT), creatine kinase, cholesterol, triglycerides and uric acid and C-Reactive Protein (CRP)] in blood
- Routine biochemistry evaluations in urine [pH, protein, glucose, ketones and blood]
- Inflammatory markers in blood [CRP] and Cerebrospinal Fluid (CSF) [protein, CSF/serum albumin ratio, IgG + IgM Index, Oligoclonal bands, glucose, cell count and differential count]
- Autoimmune antibodies in blood [Anti-nuclear Antibodies (ANA), Anti-double stranded DNA Antibodies (Anti-dsDNA)]
- Serology (HIV-1/2 Antibody, Hepatitis B Virus Surface Antigen, Hepatitis C Virus Antibody, Rapid Plasma Reagin (syphilis))

Statistical Analysis Plan Version Date: 05-Dec-2023

 Other laboratory tests (U1-nRNP Ab, Anti-Ro (SS-A Ab), Anti-La (SS-B Ab), Complement C1q Antibody, C3c, Complement C4)

The actual values and change from baseline, see Sections 8.2 and Section 8.3 for definitions, for all continuous laboratory parameters above will be summarized per treatment group, by visit [Baseline, Visit 2 (Week 2), Visit 3 (Week 8), Visit 4 (Week 10), Visit 5 (Week 24), Visit 6 (Week 26), Visit 7 (Week 36), Visit 8 (Week 48), Visit 9 (Week 50), Follow-up Visit 10 (Week 67) and Follow-up Visit 11 (Week 74)] [TFL Shell Table 14.3.3.1.1, 14.3.3.2.1, 14.3.3.3.1.1]. Urinalysis categorical data will be summarized separately [TFL Shell Table 14.3.3.1.2]. Serology data, Vitamin B12, folate and thyroid function tests are collected at screening only [TFL Shell Table 14.3.3.4].

Shift tables will present shift from baseline to each subsequent post-baseline visit, i.e. Baseline, as defined in section 8.2 [TFL Shell Table 14.3.3.1.2, 14.3.3.2.2, 14.3.3.3.2].

A box plot will present Hematology and Biochemistry laboratory values per Visit and Treatment Group [TFL Shell Figure 14.4.1, 14.4.2].

All laboratory data will be listed [TFL Shell Listing 16.2.8.1, 16.2.8.2, 16.2.8.3, 16.2.8.4, 16.2.8.5, 16.2.8.6].

For Haematology, Chemistry. Coagulation, Urinalysis, Immunochemistry. Molecular Biology as per the vendor instructions. if the lab results are reported below the lower limit of quantification (LLOQ), then the value used in summaries could be LLOQ/2, i.e. if the result is reported as "<0.5", then 0.25 will be used. For results reported as above the upper limit of quantification (ULOQ), then the ULOQ could be used, i.e. if the result is ">54.4", then 54.4 will be used. Laboratory data will be listed as per the original result provided by the vendor.

#### 11.5.3 Vital Signs

Vital signs will be measured at each visit. During dosing visits, vital signs (Systolic/Diastolic Blood Pressure (SBP/DBP), Heart Rate, Respiratory Rate and Temperature, Weight) will be measured before and after the administration of study vaccine (except weight which is measured as part of the Physical and Neurological Examination in the eCRF but will be analysed as part of vital signs). At Visit 1 (Week 0), measurements will be made just before the first injection (time 0) and at the following times after the injection at 1, 2, 4, 8, 12, and 24 hours. On subsequent dosing visits [Visit 3 (Week 8), Visit 5 (Week 24) and Visit 8 (Week 48)], measurements will be done at time 0, 1, 2, and 4 hours.

Blood Pressure and Heart Rate will be measured in the sitting and standing positions at the screening visit and at time 0 of Visit 1 (Week 0). The sitting blood pressure should be measured first and should be measured after the subject has been sitting down for at least 5 minutes. The subject should then be asked to stand and the standing blood pressure should be measured after the subject has been standing for 2 minutes. At all other timepoints for Visit 1 (Week 0) or for all other visits, blood pressure and heart rate will be measured in the sitting position only.

Blood pressures will be measured with a standardized mercury manometer; alternative validated methods of measurement may also be used. The point of disappearance of Korotkoff sounds (phase V) will be recorded as the diastolic blood pressure where a sphygmomanometer is used. Heart rate will be determined over 60 seconds following the recording of blood pressure in the corresponding position.

For vital signs parameters the change from baseline value is defined as the value at any given postbaseline timepoint minus the baseline value, i.e. post-baseline value – baseline value, for no dosing visits. For the post-dose vital signs at dosing visits instead of the change from baseline, the change from the last pre-dose assessment will be calculated, i.e. post-baseline value at dosing visit x – last pre-dose value at dosing visit x. All vital signs parameters [SBP, DBP, Heart Rate, Respiratory Rate and Temperature] actual values and change from baseline, in addition for dosing visits the change from the last pre-dose assessment on the dosing visit, will be summarized by Visit, Timepoint, Position and Treatment Group [TFL Shell Table 14.3.4.1].

For example for Visit 3 we will have:

Visit 3 timepoint 1 hour post-dose and change from Visit 3 timepoint 0 hours Visit 3 timepoint 2 hours post-dose and change from Visit 3 timepoint 0 hours Visit 3 timepoint 4 hours post-dose and change from Visit 3 timepoint 0 hours

The normal ranges for vital sign parameters are as follows:

Measurement (unit)	Minimum	Maximum
Diastolic Blood Pressure (mmHg)	40	130
Heart Rate (beats per minute)	40	140
Systolic Blood Pressure (mmHg)	80	200
Temperature (°C)	35	40
Respiratory Rate (breaths/min)	10	25

Shift table categorizing results as low, normal or high based on the normal ranges above will present shift from baseline to each subsequent post-baseline visit, i.e. Baseline, as defined in Section 8.2 [TFL Shell Table 14.3.4.2].

A box plot will present vital signs values by Visit and Treatment Group [**TFL Shell Figure 14.5.1**]. In case of multiple timepoints per visit, only the last timepoint in the respective visit will be included.

All vital signs data will be listed for the Intention-to Treat Population [TFL Shell Listing 16.2.9].

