5.3.5.3 Other Variables Related to Safety

The following variables will be included in the analyses:

- 1) Routine hematology and biochemistry evaluations in blood
- 2) Routine biochemistry evaluations in urine
- 3) Inflammatory markers in blood and CSF
- 4) Autoimmune antibodies in blood
- 5) Physical examination results
- 6) Neurological examination results
- 7) Vital signs
- 8) Brain imaging (MRI) results
- 9) Electrocardiograms

Endpoints 1-4:

All laboratory parameters will be summarized per dose group and measurement time point. Change from baseline will be presented per dose group at Visit 11 [Week 74]. Shift tables will present shift from baseline [Week 0] to Visit 9 [Week 50].

A box plot will present laboratory values per measurement time and dose group.

Endpoints 5-6:

Data will be summarized per measurement time and dose group.

Endpoint 7:

Vital signs will be presented as described for laboratory parameters.

Endpoints 8-9:

Data will be summarized per measurement time and dose group.

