# 7.0 Study Endpoints

## 7.1 Primary Endpoints

The primary focus of this study is the assessment of safety and tolerability of ACI-35.030 and JACI-35.054. Safety and tolerability will be assessed by examination of a number of endpoints:

- Adverse events
- Immediate and delayed reactogenicity (e.g. anaphylaxis, local and systemic reactogenicity, including immune-complex disease)
- Suicidal ideation as assessed by Columbia-Suicide Severity Rating Scale (C-SSRS)
- Behavior as assessed by Neuropsychiatric Inventory Scale (NPI)
- Cognitive and functional assessments (RBANS, CDR-SB)
- Vital signs
- Magnetic Resonance Imaging (MRI) imaging
- Electrocardiogram
- Routine hematology and biochemistry evaluation in blood and urine
- Evaluation of autoimmune antibodies including anti-DNA antibodies in blood
- Inflammatory markers in blood and CSF

The immune response (i.e. immunogenicity) will be assessed by:

• Anti-pTau IgG and Anti-ePHF IgG titers in serum (e.g. geometric mean, change from baseline, responder rate, peak and area under the curve)

**Note**: anti-pTau IgG means the antibody response generated against pathological Tau species. This umbrella denomination includes anti-pTau IgG and anti-ePHF IgG responses.

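### The vital-sign shift table uses limits so wide (for example 35 to 40 °C) that readings such as 39.5 °C, 195/125 mmHg or 135 bpm are tabulated as normal

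*SAP*

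**What the plan says.** SAP 11.5.3 introduces its limits with the words "The normal ranges for vital sign parameters are as follows". Among them are "Temperature (°C) 35 40", "Systolic Blood Pressure (mmHg) 80 200" and "Diastolic Blood Pressure (mmHg) 40 130". Heart rate is 40 to 140 bpm and respiratory rate 10 to 25 breaths per minute. These limits feed shift Table 14.3.4.2: "Shift table categorizing results as low, normal or high based on the normal ranges above will present shift from baseline to each subsequent post-baseline visit". The title in SAP Appendix 2 shows that this table is laid out by visit, timepoint and position.

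The other final vital-sign outputs are:

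- Table 14.3.4.1, a continuous summary by visit, timepoint, position and treatment group. Under SAP 11.0 it includes quartiles, minimum and maximum.
- Figure 14.5.1, a box plot, for which the SAP says: "In case of multiple timepoints per visit, only the last timepoint in the respective visit will be included".
- Listing 16.2.9, which holds all the readings.

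The protocol gives no competing ranges. Section 5.3.5.3 says only: "Vital signs will be presented as described for laboratory parameters". SAP 7.1 lists vital signs among the primary safety endpoints, and also "Immediate and delayed reactogenicity (e.g. anaphylaxis, local and systemic reactogenicity, including immune-complex disease").

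**The concern.** A shift table is where a reader looks to see how many subjects moved out of the reference range after an injection. Calling 35 to 40 °C normal means that a subject who becomes clearly febrile after vaccination stays in the normal column. The same holds for large rises in blood pressure and heart rate. It also holds on the low side: a fall to 82/42 mmHg is tabulated as normal, although anaphylaxis is named in the reactogenicity endpoint.

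No other final vital-sign output counts subjects above or below any threshold. By contrast, SAP 11.5.4 does give threshold counts for QTc. A row of normal-to-normal entries at each dose could be read as evidence of tolerability when, within these limits, the table had no way of showing anything else.

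**Working it through.** **The plan's own figures.** The SAP gives no calculated figure for vital signs. The group size used below, 6 active subjects in an initial sub-cohort, comes from SAP 6.1, and the safety figures given there reproduce:

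- Chance of at least one event in 6: 1 − 0.99^6 = 5.85% and 1 − 0.90^6 = 46.86% (stated as 6% and 47%).
- Upper bound when none is seen: 1 − 0.20^(1/6) = 23.5% and 1 − 0.10^(1/6) = 31.9% (stated as 24% and 32%).

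These figures are not inputs to the point.

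**Step 1: apply the SAP limits.** Rule: low if below the minimum, high if above the maximum, otherwise normal. The SAP does not say how a value exactly on a limit is classed; it is taken here as normal.

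| Parameter | SAP limits | Classed normal | First value tested that is classed high |
|---|---|---|---|
| Temperature (°C) | 35 to 40 | 38.0, 38.5, 39.0, 39.5, 40.0 | 40.1 |
| Systolic (mmHg) | 80 to 200 | 160, 180, 200 | 201 |
| Diastolic (mmHg) | 40 to 130 | 100, 120, 130 | 131 |
| Heart rate (bpm) | 40 to 140 | 110, 130, 140 | 141 |

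So 36.6 to 39.5 °C, 125/75 to 195/125 mmHg and 70 to 135 bpm are each tabulated normal to normal.

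**Step 2: what this does to a count.** The documents define no cut-off for fever, so a range is assumed. Take a made-up group of 6 active subjects, all normal at baseline, with post-dose temperatures of 36.7, 37.2, 38.1, 38.6, 39.2 and 39.8 °C.

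| Upper limit (°C) | Subjects shifting normal to high |
|---|---|
| 40.0 (SAP) | 0 of 6 |
| 39.0 (assumed) | 2 of 6 |
| 38.5 (assumed) | 3 of 6 |
| 38.0 (assumed) | 4 of 6 |
| 37.5 (assumed) | 4 of 6 |

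**Step 3: what the continuous table shows for the same group.** Mean = 229.6 / 6 = 38.27, median = (38.1 + 38.6) / 2 = 38.35, maximum = 39.8 °C. The reaction is visible there, but not as a count of subjects.

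**Step 4: what the box plot keeps.** SAP 11.5.3 plans post-dose readings at 1, 2, 4, 8, 12 and 24 h at Visit 1 (6 readings), and at 1, 2 and 4 h at Visits 3, 5 and 8 (3 each). That is 6 + 3 × 3 = 15 post-dose readings per subject. Keeping only the last of each visit leaves 4 (24 h once, 4 h three times) and drops 15 − 4 = 11, including every 1 h and 2 h reading.

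**The case against.** The strongest reply is that these readings are reported elsewhere.

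- Table 14.3.4.1 prints the minimum and maximum at each timepoint, and the change from the same visit's pre-dose value. With 6 active subjects, one reading of 39.5 °C is the printed maximum unless another is higher.
- Listing 16.2.9 holds every reading.
- Abnormal findings judged clinically significant become adverse events (protocol 4.1.4, SAP 8.10). These are counted by treatment group, severity and relationship. Telephone contact 48 to 72 hours after each injection and a subject diary support their capture.
- The DSMB receives vital-sign box plots, one covering the first 24 hours, and a vital-signs listing.
- Table 14.3.4.2 is produced for the final analysis only. The dosing suspension rules run on adverse events and DSMB review.

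All of this stands, and it limits the consequence. It does not repair the table. A minimum and maximum at one timepoint do not say how many subjects were affected, and they do not link readings within a subject. A listing summarises nothing by dose. Adverse event capture depends on the investigator's judgement. The DSMB outputs serve monitoring and are not in the final-analysis list.

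A reader might infer more: that fever or marked hypertension would go unreported, that safety monitoring is weakened, or that the shift table is bound to show no shifts to high. The documents support none of these. Values beyond the limits are still classed high, respiratory rate sits in the same table with an upper limit of 25, and the early post-dose readings remain in both tables. The limits resemble data-entry checks, but no passage says that they are.

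**Conclusion.** The point holds for one end-of-study table. Within the stated limits, Table 14.3.4.2 classes readings such as 39.5 °C, 195/125 mmHg or 135 bpm as normal, and it is the only categorical vital-sign summary of a primary safety endpoint in the final analysis. In the illustration, the effect is 0 of 6 shifts to high instead of 2 to 4 of 6. That size rests on invented temperatures and assumed cut-offs, but the classification itself follows directly from the SAP rule and holds for every assumed cut-off from 37.5 to 39.0 °C. The box plot adds little, because it omits the earlier post-dose readings.

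No reading is lost, and no estimate, test, dosing rule or escalation step depends on this table. It is a misleading descriptive output that should be fixed before unblinding; it does not threaten the trial's safety oversight.

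**What to change.** Amend SAP 11.5.3 before unblinding, because categories chosen afterwards would look data-driven.

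1. Replace the limits used for Table 14.3.4.2 with pre-specified reference categories set by the medical monitor. Any number, such as 38.0 °C for temperature, is an assumed analysis category and not a rule for managing subjects. Keep the present limits only as data checks, and stop calling them normal ranges.
2. For dosing visits, also classify each subject's post-dose maximum and minimum over all timepoints, with counts and percentages by treatment group.
3. Show all post-dose timepoints in Figure 14.5.1.

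The cost is SAP wording and a little reprogramming of one table and one figure, on data already collected. The downside is that more values will be flagged, some of them minor.

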#### 11.5.4 Electrocardiogram (ECG)

12-lead ECG recording machines will be provided by the central reading company **Exercise**. Printouts of each ECG must be kept at the site for archiving. **We will manage ECG data** through their Web-based platform. The system allows the acquisition, storage and display of ECG

recordings from the ECG machines so that cardiologists can review them. Please refer to the ECG manual for further details.

Normal, abnormal not clinically significant and abnormal clinically significant results as interpreted by the site will be summarized by Visit (Baseline, as defined in Section 8.2) and Treatment Group (and Overall) [TFL Shell Table 14.3.5.1].

ECG parameters [PR interval (msec), RR interval (msec), QRS duration (msec), QT Interval (msec), QTcB Interval (msec) and QTcF interval (msec)] actual values and change from baseline where baseline and change from baseline are as defined in Section 8.2 and Section 8.3, will be summarized by Visit, and Treatment Group (and overall) [TFL Shell Table 14.3.5.2].

The number and percentage of subjects with an absolute QTcB Interval (msec) ≤480 or >480; and an absolute QTcF interval (msec) ≤480 or >480 will be summarized by Visit, and Treatment Group (and overall) [TFL Shell Table 14.3.5.3].

The number and percentage of subjects with a change from baseline in QTcB Interval (msec) and QTcF interval (msec) <30 or  $\geq$ 30 or  $\geq$ 60 will be summarized by Visit, and Treatment Group (and overall) [TFL Shell Table 14.3.5.4].

Shift table categorizing results as normal, abnormal (clinically significant / not clinically significant) will present shift from baseline to each subsequent post-baseline visit, i.e. Baseline, as defined in Section 8.2 [TFL Shell Table 14.3.5.5].

All ECG data will be listed for the Intention-to Treat Population [TFL Shell Listing 16.2.10.1 and 16.2.10.2].

#### **11.5.5 Physical Examinations**

A physical examination including the assessment of general appearance, the head, eyes, ears, nose, throat, heart, chest, lungs, abdomen, lymph nodes, extremities, peripheral pulses, skin and any other physical conditions of note is to be conducted at each visit [Screening, Visit 1 (Week 0), Visit 2 (Week 2), Visit 3 (Week 8), Visit 4 (Week 10), Visit 5 (Week 24), Visit 6 (Week 26), Visit 7 (Week 36), Visit 8 (Week 48), Visit 9 (Week 50), Follow-up Visit 10 (Week 67) and Follow-up Visit 11 (Week 74)].

A summary of physical examination finding will be presented by treatment group (and overall for each main cohort) and visit for the Intention-to Treat Population [TFL Shell Table 14.3.6.1].

A shift table will present shift from baseline to each subsequent post-baseline visit, i.e. Baseline, as defined in section 8.2 [TFL Shell Table 14.3.6.2].

Any clinically significant abnormalities identified after the subject signs the ICF and up to the last safety follow-up visit will be recorded on the AE eCRF and summarized as outlined in SAP Section 11.5.1. Any clinically significant abnormality that was pre-existing at the time of signing the ICF will be recorded on the Medical History eCRF and summarized as outlined in SAP Section 11.3.

Physical examination data will be listed for the ITT Population [TFL Shell Listing 16.2.11].

## **11.5.6 Neurological Examinations**

Neurological examination data including the examination of the cranial nerves, upper and lower extremities for muscle strength, reflexes, sensation and cerebellar function will be conducted at each visit [Screening, Visit 1 (Week 0), Visit 2 (Week 2), Visit 3 (Week 8), Visit 4 (Week 10), Visit 5 (Week 24), Visit 6 (Week 26), Visit 7 (Week 36), Visit 8 (Week 48), Visit 9 (Week 50), Follow-up Visit 10 (Week 67) and Follow-up Visit 11 (Week 74)] [TFL Shell Table 14.3.7.1].

Data will be summarized by treatment group (and overall for each main cohort) and visit for the ITT Population.

A shift table will present shift from baseline to each subsequent post-baseline visit, i.e. Baseline, as defined in section 8.2 [TFL Shell Table 14.3.7.2].

All neurological examination data will be listed [TFL Shell Listing 16.2.11].

#### 11.5.7 Magnetic Resonance Imaging (MRI)

Brain MRI scans will be conducted according to the schedule of assessments, see **Figure 2** above, and examined for evidence of encephalitis and other brain pathology. Scans will be systematically analyzed e.g. for the presence of micro hemorrhages or vasogenic edema by the Central reading company (

Normal, abnormal not clinically significant and abnormal clinically significant results as interpreted by the site will be summarized by Visit (Baseline, as defined in section 8.2) and Treatment Group (and Overall) for the ITT Population [TFL Shell Table 14.3.8.1].

MRI results will be summarized by Visit (Baseline, as defined in section 8.2) and Treatment Group (and Overall) for the ITT Population [TFL Shell Table 14.3.8.2].

Any clinically significant abnormalities identified after the subject signs the ICF and up to the last safety follow-up visit will be recorded on the AE eCRF and summarized as outlined in section 11.5.1. Any clinically significant abnormality that was pre-existing at the time of signing the ICF will be recorded on the Medical History eCRF and summarized as outlined in section 11.3.

All MRI data will be listed [TFL Shell Listing 16.2.7.7.1].

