- 14. Use of diltiazem unless on a stable dose for at least 3 months prior to screening.
- 15. Significant risk of suicide defined, using the Columbia-Suicide Severity Rating Scale, as the subject answering: "yes" to suicidal ideation questions 4 or 5 or answering: "yes" to suicidal behavior within the past 12 months.
- 16. Concomitant psychiatric or neurologic disorder other than those considered to be related to AD (e.g. head injury with loss of consciousness, symptomatic stroke, Parkinson's disease, severe carotid occlusive disease, TIAs).
- 17. History or presence of uncontrolled seizures. If history of seizures, they must be well controlled with no occurrence of seizures within 2 years prior to screening. The use of anti-epileptic medications is permitted if at stable dose for at least 3 months prior to screening.
- 18. History of meningoencephalitis within the past 10 years prior to screening.
- 19. Subjects with a history of hemorrhagic and/or non-hemorrhagic stroke.
- 20. Presence or history of peripheral neuropathy.
- 21. History of inflammatory neurological disorders with potential for CNS involvement.
- 22. Screening MRI scan showing structural evidence of alternative pathology not consistent with AD which could cause the subject's symptoms. Evidence of space occupying lesions other than benign meningioma of less than 1 cm diameter, more than two lacunar infarcts or one single infarct larger than 1 cm in diameter or any single area of superficial siderosis or evidence of a prior macro-hemorrhage ≥10 mm. Microbleeds on T2* MRI are allowed up to a maximum of 10, regardless of the location.
- 23. MRI examination cannot be done for any reason, including but not limited to metal implants contraindicated for MRI studies and/or severe claustrophobia.
- 24. Significant hearing or visual impairment or other issues judged relevant by the investigator preventing to comply with the protocol and to perform the outcome measures.

📿 AC Immune

- 25. Clinically significant infections or major surgical operation within 3 months prior to screening. Planned surgery anticipated to occur during participation in the study must be reviewed and approved by the medical monitor at screening.
- 26. Any vaccine received within the past 2 weeks before screening, including influenza vaccine.
- 27. Clinically significant arrhythmias or other clinically significant abnormalities on ECG at screening.

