5.3.5 Safety Analyses

The primary safety endpoints are type, frequency and intensity of AEs evaluated until the end of treatment and change from baseline in the parameters of physical and neurological examination, vital signs, MRI imaging, ECG, routine hematology and biochemistry evaluation in blood and urine, evaluation of autoimmune antibodies in blood and inflammatory markers in blood and CSF. Other cognitive and clinical variables related to safety are described below.

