## 11.5 Safety Analyses

The primary safety endpoints are type, frequency, and intensity of AEs evaluated until the end of treatment and change from baseline in the parameters of physical and neurological examination, vital signs, MRI imaging, Electrocardiogram (ECG), routine hematology and biochemistry evaluation in blood and urine, evaluation of autoimmune antibodies in blood and inflammatory markers in blood and CSF. Other cognitive and clinical variables related to safety are provided in Section 5.3.5.1 and Section 5.3.5.3 of the study protocol. Continuous and categorical laboratory data will be summarized separately.

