Table 14.3.5.3 Centrally Read Electrocardiogram (ECG) Categorical Analysis of QTc by Visit (Intention-to-Treat Population)   Table 14.3.5.4 Centrally Read Electrocardiogram (ECG) Categorical Analysis of QTc Change from Baseline by Visit (Intention-to-Treat			X
			X
Table 14.3.5.5 Shift from Baseline Centrally Read Electrocardiogram (ECG) Interpretation by Visit (Intention-to-Treat Population)			X
Table 14.3.6.1 Physical Examination by Visit (Intention-to-Treat Population)		├ ────┼	Х
Table 14.3.6.2 Shift from Baseline Classification of Physical Examination Results by Visit (Intention-to-Treat Population)			Х
Table 14.3.7.1 Neurological Examination by Visit (Intention-to-Treat Population)			Х
Table 14.3.7.2 Shift from Baseline Classification of Neurological Examination Results by Visit (Intention-to-Treat Population)			Х
Table 14.3.8.1 Magnetic Resonance Imaging (MRI) by Visit (Intention-to-Treat Population)			Х
Table 14.3.8.2 Magnetic Resonance Imaging (MRI) Results by Visit (Intention-to-Treat Population)   Table 14.3.8.3 Volumetric MRI Analyses by Brain Region (Whole Brain, Intracranial, Hippocampus and Ventricles) (Intention-to-Treat			 
Population)			Х
Table 14.3.9 Clinical Dementia Rating Scale-Sum of Boxes (CDR-SB) and Change from Baseline by Visit (Intention-to-Treat Population)   Table 14.3.10 Repeatable Battery for the Assessment of Neuropsychological Status (RBANS) Total Scale Score and Change from		┝────┼	Х
Baseline by Visit (Intention-to-Treat Population)			Х
Table 14.3.11.1 Neuropsychiatric Inventory (NPI) Total Score and Change from Baseline by Visit (Intention-to-Treat Population)			Х
Table 14.3.11.2 Neuropsychiatric Inventory (NPI) Total Distress Score and Change from Baseline by Visit (Intention-to-Treat Population)			Х
Table 14.3.12 Columbia-Suicide Severity Rating Scale (C-SSRS) by Visit (Intention-to-Treat Population)			Х
Table 14.3.13 Subject Capacity to Consent: MacCAT-CR by Visit (Intention-to-Treat Population)			Х
Figure 14.1.1.1 Geometric Mean Time Course of Anti-pTau IgG Titer by Treatment Group (Intention-to-Treat Population)	х	х	Х
Figure 14.1.1.1.1 Geometric Mean Time Course of Anti-pTau IgG Titer by Treatment Group (Y-axis adjusted) (Intention-to-Treat Population)	x		х
Figure 14.1.1.1.2 Geometric Mean Time Course of Change from Baseline of Anti-pTau IgG Titer by Treatment Group (Intention-to-Treat Population)			х

Statistical Analysis Plan

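### MRI safety is defined as change from baseline, but the summary tables as described show status by visit and do not give the number of subjects with new findings

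*SAP*

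**What the plan says.** MRI imaging is among the primary safety endpoints (Protocol 2.2.1, SAP 7.1). Protocol 5.3.5 states the measure as "change from baseline in the parameters of physical and neurological examination, vital signs, MRI imaging, ECG" and further assessments, and SAP 11.5 repeats it almost word for word.

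SAP 11.5.7 describes two safety summaries of the scans:

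- Table 14.3.8.1: "Normal, abnormal not clinically significant and abnormal clinically significant results as interpreted by the site will be summarized by Visit" and treatment group.
- Table 14.3.8.2: "MRI results will be summarized by Visit (Baseline, as defined in section 8.2) and Treatment Group (and Overall) for the ITT Population".

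Appendix 2 lists them as "Table 14.3.8.1 Magnetic Resonance Imaging (MRI) by Visit (Intention-to-Treat Population") and "Table 14.3.8.2 Magnetic Resonance Imaging (MRI) Results by Visit (Intention-to-Treat Population"). Protocol 5.3.5.3 likewise plans only a summary per time point and dose group for MRI. The central reader is to examine scans systematically, for example for the "presence of micro hemorrhages or vasogenic edema by the Central reading company".

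On entry, Protocol 3.3.2 says: "Microbleeds on T2* MRI are allowed up to a maximum of 10, regardless of the location". It excludes lacunar infarcts only when there are more than two.

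Two other outputs carry MRI information. Listing 16.2.7.7.1 shows all MRI data by subject. Abnormalities judged clinically significant are recorded as adverse events and tabulated there.

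**The concern.** A change-from-baseline endpoint asks which subjects have something on a later scan that was absent from the first. Two columns of status counts answer that only if nobody was abnormal at the start, and the entry criteria make that unlikely to hold here.

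The protocol names central nervous system inflammation as a theoretical risk of these vaccines and directs investigators to the MRI scans as part of watching for it (Protocol 1.5.1). A reader of the final report will want to know, for each dose group, how many subjects had any new finding. As described, the summary tables do not supply that number.

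**Working it through.** **1. The plan's own safety figures.** The documents state no figure for MRI. The nearest is the adverse event reasoning for 6 active subjects in Protocol 5.3.1 and SAP 6.1.

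- Chance of at least one event, 1 − (1 − p)^6: for p = 1%, 1 − 0.99^6 = 5.9%; for p = 10%, 1 − 0.90^6 = 46.9%. Stated: 6% and 47%.
- Upper bound with no events, 1 − (1 − c)^(1/6): for c = 80%, 23.5%; for c = 90%, 31.9%. Stated: 24% and 32%.

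All four reproduce. Each depends on knowing how many of the 6 subjects newly had the event. That is the count to look for in the MRI outputs.

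**2. Planned outputs side by side (SAP 11.5.2 to 11.5.7 and Appendix 2).**

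| Safety assessment | By-visit summary | Shift from baseline |
|---|---|---|
| Haematology, biochemistry, urinalysis | yes | 14.3.3.1.2, 14.3.3.2.2, 14.3.3.3.2 |
| Vital signs | yes | 14.3.4.2 |
| ECG | yes | 14.3.5.5 |
| Physical examination | yes | 14.3.6.2 |
| Neurological examination | yes | 14.3.7.2 |
| MRI (safety) | 14.3.8.1, 14.3.8.2 | none |

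ECG uses the same three rating categories as Table 14.3.8.1. The one MRI table of change, 14.3.8.3, is exploratory volumetry (SAP 11.7.4) and does not cover microbleeds, oedema or infarcts.

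**3. What by-visit counts can and cannot tell.** Let n subjects be scanned at both times, b abnormal at baseline and f abnormal at the later visit. From the two totals alone, the number newly abnormal lies between max(0, f − b) and min(f, n − b). The documents give no baseline abnormality rate, so b and f below are assumptions. The value 18 is the planned maximum on active treatment in an expanded sub-cohort (6 + 12).

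| n | b | f | Newly abnormal |
|---|---|---|---|
| 6 | 2 | 2 | 0 to 2 (0 to 33%) |
| 6 | 3 | 3 | 0 to 3 (0 to 50%) |
| 6 | 3 | 4 | 1 to 3 (17 to 50%) |
| 18 | 6 | 6 | 0 to 6 (0 to 33%) |
| 18 | 9 | 9 | 0 to 9 (0 to 50%) |

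A shift table replaces each range with the exact number.

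**4. Worsening within the abnormal category.** Take a subject rated abnormal but not clinically significant at screening with 2 microbleeds, who later has 9 and keeps that rating. No cell of Table 14.3.8.1 changes. A shift table does not show it either, because the category is the same at both times. On assumed counts, if 3 of 6 subjects have microbleeds at screening and 2 of those 3 gain more, presence reads 3/6 then 3/6, while 2/6 (33%) have new microbleeds. Only a count of new findings shows this.

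**5. Changing denominators.** Visit 6 includes MRI (Protocol 3.5.2.12). In sub-cohort 1.1 it was replaced by a remote visit in 7 of 8 subjects (SAP 12.0), leaving 8 − 7 = 1 on-site visit. Protocol 3.5.1.1 also lets scans be postponed or cancelled under Covid-19 restrictions. By-visit proportions can therefore move because the set of scanned subjects moved. A summary over any post-baseline scan is less exposed to this.

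**The case against.** The case for leaving the plan alone has substance.

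- **Every scan is listed.** With 6 active subjects per initial dose group, Listing 16.2.7.7.1 can be read directly, and the DSMB shell list in Appendix 2 includes a brain MRI listing. A reader might infer that new lesions would be hidden from the report. The documents do not support that: the gap is in the summary tables. It still matters, because sub-cohort 1.2 has 25 subjects with five scheduled scans each (screening and Visits 4, 6, 9 and 11), up to 25 × 5 = 125 scans to compare by eye.
- **Clinically significant findings become adverse events.** This stands, and under Protocol 4.1.4 it includes baseline abnormalities that worsen. It leaves out findings judged not significant.
- **The table shells are a separate document.** The rows of Table 14.3.8.2 cannot be seen and might hold lesion counts. One cannot assert that the table shows only presence or absence. Neither its title nor the SAP text, however, promises a comparison within subject.
- **The SAP follows Protocol 5.3.5.3.** True, but that section plans the same kind of by-visit summary for ECG, physical and neurological examination, and the SAP added shift tables for those three. SAP 12.0 gives no reason for treating MRI differently.

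A reader might also infer that new oedema would be masked by old oedema. No section shows that pre-existing oedema is expected; the entry criteria do not mention it, and clinically significant oedema would be an adverse event. Nor does superficial siderosis need much attention: any area of it excludes a subject at entry, so siderosis seen later is already new.

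**Conclusion.** The point holds for the summary tables as described. The endpoint is defined as change from baseline, and neither listed MRI safety table is described as giving a within-subject change or a count of subjects with new findings. The part affected is new findings judged not clinically significant, chiefly added microbleeds, which would appear only in the subject listing.

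The size cannot be estimated from the documents. Under the assumption that half the subjects are abnormal at both times, the by-visit totals fit anything from none to half being newly abnormal, whether n is 6 or 18. These counts are illustrative. The conclusion also assumes that the unseen shells add no within-subject comparison to Table 14.3.8.2.

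This is a reporting gap that should be closed before the final tables are programmed. It does not show that safety monitoring during the trial was blind to new lesions.

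**What to change.** In SAP 11.5.7 and Appendix 2:

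- **(a)** Add a shift table for the Table 14.3.8.1 categories, baseline versus each post-baseline visit and versus the worst post-baseline rating, in the form of ECG Table 14.3.5.5.
- **(b)** Add a table, by treatment group, of the number and percentage of subjects with at least one new finding versus the screening scan, at each visit and at any post-baseline scan. Rows: increase in microbleed count, new vasogenic oedema, new infarct, other new lesion. Denominator: subjects with at least one post-baseline scan. Source: the central read, where it records these items.

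Both are needed, because (a) alone misses added microbleeds in a subject already rated abnormal.

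The cost is two programmed tables and no new scans. One check comes first: the documents do not say that the central-read transfer holds post-baseline lesion counts. If it does not, (b) should be limited to the items it does hold, and the SAP should say so.
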